REPRISE II: Repositionable Percutaneous Replacement of Stenotic Aortic Valve through Implantation of Lotus™ Valve System – Evaluation of Safety and Performance	
	
 
○ Grade of aortic valve regurgitation: paravalvular, central and combined
 
● Device Success based on the Valve Academic Research Consortium definitions (VARC)a, b
 
 
Note: At least 1 echocardiogram must be obtained before discharge or 7 days (whichever comes first); if multiple echocardiographic studies are performed prior to discharge and within 7 days of the procedure, the latest study performed will be used for analysis.
 
a: Kappetein AP, et al. J Am Coll Cardiol. 2012;60:1438                      b: Leon MB, et al. J Am Coll Cardiol. 2011;57:253

Additional Measurements	
Additional measurements based on the VARCa,b endpoints and definitions (see Table 26.2-1 for definitions) will be collected peri- and post-procedure, at discharge or 7 days post-procedure (whichever comes first), 30 days, 3 months, 6 months, and 1, 2, 3, 4, and 5 years post index procedure, unless otherwise specified below.
 
 
● Safety endpoints adjudicated by an independent Clinical Events Committee (CEC):                             
 
○ Mortality: all-cause, cardiovascular, and non-cardiovascular
 
○ Stroke: disabling and non-disabling
 
○ Composite of all-cause mortality and disabling stroke
 
○ Myocardial infarction (MI): periprocedural (≤72 hours post index procedure) and spontaneous (>72 hours post index procedure)
 
○ Bleeding: life-threatening (or disabling) and major
 
○ Acute kidney injury (≤7 days post index procedure): based on the AKIN System Stage 3 (including renal replacement therapy) or Stage 2
 
○ Major vascular complication
 
○ Repeat procedure for valve-related dysfunction (surgical or interventional therapy)
 
○ Hospitalization for valve-related symptoms or worsening congestive heart failure (NYHA class III or IV)
 
○ New permanent pacemaker implantation resulting from new or worsened conduction disturbances (including new left bundle branch block [LBBB] and third degree atrioventricular block)
 
○ New onset of atrial fibrillation or atrial flutter
 
 
 

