### 11.8. *Post-Procedure*

The following are to be performed post-procedure.

- Per society guidelines, antiplatelet therapy with aspirin and a thienopyridine is recommended to decrease the risk of thrombotic or thromboembolic complications if there are no contraindications to these medications. Subjects must be treated with aspirin and clopidogrel for at least 1 month following valve implantation. If the study-specific dosages and durations for antiplatelet medications conflict with country-specific labeling for the medications, the country-specific labeling should take precedence.
  - After the Lotus Valve implant procedure, aspirin (recommended dose of  $\geq 75$  mg daily) must be given for at least 1 month. It is recommended that daily aspirin be given indefinitely thereafter as per local standard of care. Aspirin doses may be adjusted to the closest approximation based on local tablet formulation availability.
  - After the Lotus valve implant procedure, clopidogrel (recommended dose of 75 mg daily) is required for at least 1 month.  
*Note:* An alternative P2Y12 inhibitor (e.g., ticlopidine) may be prescribed as an alternative if subject is allergic to or intolerant of clopidogrel.
  - If the subject requires chronic anticoagulation (e.g., warfarin, dabigatran, etc.), either clopidogrel or aspirin is required in addition to the anticoagulant therapy post-procedure (but both aspirin and clopidogrel are not required).
- Prophylactic antibiotic regimen should be completed as per local practice.
- Additional medications may be used at the investigator's discretion.
- It is recommended that the subject's heart rhythm be monitored using telemetry for at least 48 hours after the index procedure.
- 12-lead ECG must be completed within 24 hours post-procedure per the ECG Core Laboratory guidelines (see study Manual of Operations) and must be forwarded to the Core Laboratory for analysis.
- Cardiac enzymes (CK is required, CK-MB or troponin if CK is elevated) must be collected twice at intervals per standard of care within 6-24 hours post-procedure.

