- Myocardial infarction (MI): periprocedural ( $\leq 72$  hours post index procedure) and spontaneous ( $> 72$  hours post index procedure)
- Bleeding events: life-threatening (or disabling), major and minor
- Acute kidney injury ( $\leq 7$  days post index procedure): based on AKIN System Stage 3 (including renal replacement therapy), Stage 2, and Stage 1
- Vascular complications: major and minor
- Repeat procedure for valve-related dysfunction (surgical or interventional therapy)
- Hospitalization for valve-related symptoms or worsening congestive heart failure (NYHA class III or IV)
- New permanent pacemaker implantation resulting from new or worsened conduction disturbances (including new left bundle branch block [LBBB] and third degree atrioventricular block)
- New onset of atrial fibrillation or atrial flutter
- Coronary obstruction (periprocedural)
- Ventricular septal perforation (periprocedural)
- Mitral apparatus damage (periprocedural)
- Cardiac tamponade (periprocedural)
- Prosthetic aortic valve malapposition, including valve migration, valve embolization, ectopic valve deployment, or transcatheter aortic valve (TAV)-in-TAV deployment
- Prosthetic aortic valve thrombosis
- Prosthetic aortic valve endocarditis

Details on the CEC events and procedures are outlined in the CEC charter. Tests and images required to adjudicate these events are specified in the event definitions (see Table 26.2-1).

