
LIVER DISEASE (SEVERE) /CIRRHOSIS
	
Any of the following:
 
 
Child-Pugh class C
 
MELD score <math>\geq 10</math>
 
Portal-caval, spleno-renal, or transjugular intrahepatic portal shunt
 
Biopsy proven cirrhosis with portal hypertension or hepatocellular dysfunction
 

MITRAL VALVE APPARATUS DAMAGE
	
Angiographic or echocardiographic evidence of a new damage to the mitral valve apparatus (chordae papillary muscle, or leaflet) during or after the TAVR procedure.

MYOCARDIAL
	
Periprocedural MI (<math>\leq 72</math> hours after the index procedure)

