**Table 26.2-1: Definitions**

Term	Definition								
INFARCTION (MI)	
 
• New ischemic symptoms (e.g., chest pain or shortness of breath) or new ischemic signs (e.g., ventricular arrhythmias, new or worsening heart failure, new ST-segment changes, hemodynamic instability, new pathological Q waves in at least two contiguous leads, or imaging evidence of new loss of viable myocardium or new wall motion abnormality)
 
-AND-
 
• Elevated cardiac biomarkers (preferably CK-MB) within 72 h after the index procedure, consisting of at least one sample post-procedure with a peak value exceeding 15× upper reference limit (troponin) or 5× for CK-MB. If cardiac biomarkers are increased at baseline (>99th percentile), a further increase of at least 50% post-procedure is required AND the peak value must exceed the previously stated limit.
 
 
Spontaneous MI (>72 hours after the index procedure) Any one of the following criteria applies.
 
 
• Detection of rise and/or fall of cardiac biomarkers (preferably troponin) with at least one value above the 99th percentile URL, together with evidence of myocardial ischemia with at least one of the following               
 
○ Symptoms of ischemia
 
○ ECG changes indicative of new ischemia [new ST-T changes or new LBBB]
 
○ New pathological Q waves in at least two contiguous leads
 
○ Imaging evidence of new loss of viable myocardium or new wall motion abnormality
 
 
 
• Sudden, unexpected cardiac death, involving cardiac arrest, often with symptoms suggestive of myocardial ischemia, and accompanied by presumably new ST-segment elevation, or new LBBB, and/or evidence of fresh thrombus by coronary angiography and/ or at autopsy, but death occurring before blood samples could be obtained, or at a time before the appearance of cardiac biomarkers in the blood.
 
• Pathological findings of an acute myocardial infarction.
 
								
NEUROLOGICAL EVENT	Any central, new neurological deficit, whether temporary or permanent and whether focal or global, that occurs after the subject emerges from anesthesia								

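### A fatal or pathology-only myocardial infarction within 72 hours, without a qualifying biomarker, meets neither MI definition and drops out of the reported MI rate

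*Combined protocol and SAP*

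**What the plan says.** The synopsis lists two MI categories among the endpoints adjudicated by the Clinical Events Committee (CEC): "Myocardial infarction (MI): periprocedural (≤72 hours post index procedure) and spontaneous (>72 hours post index procedure"). Sections 7.3 and 21.1 repeat the same split, and no third category exists.

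Table 26.2-1 defines them differently.

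- **Periprocedural MI, 72 hours or less.** Two conditions joined by AND. The first is new ischemic symptoms or signs. The second is "Elevated cardiac biomarkers (preferably CK-MB) within 72 h after the index procedure, consisting of at least one sample post-procedure", with a peak above 15 times the upper reference limit (troponin) or 5 times (CK-MB).
- **Spontaneous MI, more than 72 hours.** Any one of three criteria is enough. One is a biomarker above the 99th percentile with evidence of ischemia. The second is sudden cardiac death with supporting findings, "but death occurring before blood samples could be obtained, or at a time before the appearance of cardiac biomarkers in the blood". The third is "Pathological findings of an acute myocardial infarction".

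Section 11.8 says cardiac enzymes "must be collected twice at intervals per standard of care within 6-24 hours post-procedure"; CK is required, and CK-MB or troponin only if CK is elevated. On adjudication, Section 21.1 says: "Tests and images required to adjudicate these events are specified in the event definitions".

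**The concern.** The first 72 hours are the period most closely tied to the procedure, yet they have the narrower rule. A blood result is indispensable there, and the criteria written for patients who die before one is available apply only later. The same sudden death, with the same findings, is an MI at 73 hours and not an MI at 71 hours.

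The table also fits poorly with itself. Its definition of cardiovascular death names MI as a cause, with no biomarker or time condition, so a subject can be adjudicated as dying of MI while no MI event is recorded. Stroke has a fatal route: a deficit shorter than 24 hours qualifies if the patient dies of it. Coronary obstruction can be diagnosed at autopsy, with biomarkers only as corroboration. Early MI has neither provision.

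At stake is the completeness of an adjudicated safety rate. Under Section 22.1.2 the Data Monitoring Committee follows the incidence of CEC events, so the undercount would reach that committee as well as the final report.

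**Working it through.** The plan gives no figure for this point, so the check is of logic, followed by one simple scaling.

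**Step 1: the rules in Table 26.2-1.**

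- Periprocedural MI = (time ≤72 h) AND (symptom OR sign) AND (troponin >15× OR CK-MB >5× the reference limit).
- Spontaneous MI = (time >72 h) AND (biomarker with ischemia OR sudden cardiac death as described OR pathology).

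The sign condition is easy to meet in a dying patient, because it includes ventricular arrhythmia and hemodynamic instability. The biomarker condition therefore decides the early cases.

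**Step 2: apply the rules.**

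| Case | Periprocedural | Spontaneous | Counted as MI? |
|---|---|---|---|
| (a) Fatal MI ≤72 h, no sample taken | biomarker fails | time fails | No |
| (b) Acute MI at autopsy ≤72 h, no qualifying biomarker | biomarker fails | time fails | No |
| (c) As (b), with symptoms or signs and a sample above threshold | met | not applicable | Yes |
| (d) As (a), with the findings the sudden-death criterion requires, or as (b), but after 72 h | not applicable | met | Yes |

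**Step 3: look for another route.** The endpoint lists in the synopsis and Sections 7.3 and 21.1, and the rest of Table 26.2-1, contain no biomarker-free route to an MI at 72 hours or less.

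**Step 4: can cases (a) and (b) occur?** The scheduled draws lie between 6 and 24 hours. A patient who dies before 6 hours may have no sample. One who infarcts and dies suddenly between 24 and 72 hours may have only samples that predate the event, since no further enzyme draw is scheduled in that interval. Any unscheduled sample within 72 hours would also qualify, so the schedule makes the gap possible but not inevitable.

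**Step 5: size per event.** Section 7.3 evaluates these measurements on all enrolled subjects. One event changes the rate by

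- combined cohort: 1/250 = 0.40 percentage points;
- main cohort: 1/120 = 0.83 percentage points.

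For scale, the four series of 599 or more patients in Table 4.1-1 report MI rates of 0.3% to 1.0%. In 250 subjects that is 0.003 × 250 = 0.75 to 0.010 × 250 = 2.5 events. The MI definitions behind those rates are not given, so this shows only that single events matter to a rate this low.

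**The case against.** The strongest reply is that nothing is lost from the safety evaluation except a second label. A reader might infer that early fatal MIs go uncounted altogether. The documents do not support that. Such a death counts in all-cause mortality, which is the primary safety endpoint (Section 7.1), in the composite of death and disabling stroke, and in the 30-day VARC safety composite. It counts as cardiovascular death where so adjudicated. Occlusion of a coronary ostium has its own CEC endpoint. MI is an additional measurement on which Section 12.1.2 plans no inference, and it is not a component of the 30-day composite. All of this stands, and it limits the point to the MI rate.

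Second, the wording was adopted deliberately: Table 27.1-1 attributes the revised definitions to the VARC-2 manuscript, and a local criterion would weaken comparability with other studies. This stands against rewriting the definition, but not against reporting an extra line beside it.

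Third, moving the sudden-death criterion unchanged into the first 72 hours could mislabel deaths. It accepts new left bundle branch block as supporting evidence, while Table 26.2-1 treats that finding as an implant-related conduction disturbance. This also stands, and it shapes the fix.

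Fourth, CEC procedures are in a charter that is not among the documents and may already address these cases. That cannot be checked here.

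**Conclusion.** The gap is real on the text. An MI at 72 hours or less that is fatal without a qualifying post-procedure biomarker, or that is shown only by pathology, is not counted as an MI event. The direction is an undercount of 0.40 points per event in 250 subjects, or 0.83 points in 120, assuming full enrollment. No hypothesis test, sample size or success criterion depends on it.

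Two stronger readings should be set aside. One is that every autopsy-proven MI within 72 hours is missed: case (c) in the working shows that one with symptoms or signs and a qualifying sample is counted. The other is that the number missed can be estimated and may equal the whole reported rate. The expected mortality gives 0.098 × 250 = 24.5 deaths by 30 days, but the documents do not say how many fall within 72 hours or how many are due to MI. Assuming 20–40% for the first and 10–30% for the second gives 24.5 × 0.2 × 0.1 = 0.5 to 24.5 × 0.4 × 0.3 = 2.9 deaths. Neither range has a source in the documents, and the product treats every such death as lacking a biomarker, so it is at most a ceiling under those assumptions.

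The conclusion rests on the CEC applying Table 26.2-1 as written, with no contrary rule in its charter.

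**What to change.** Keep the periprocedural MI rate exactly as now defined, so that it remains comparable with other VARC-based reports. In Table 26.2-1 and the CEC charter, add a separately reported line, with a combined total, for MI at 72 hours or less established by either of the following:

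- (a) pathological findings of acute MI; or
- (b) sudden cardiac death before a sample could be obtained, with new ST-segment elevation or fresh coronary thrombus. New left bundle branch block alone should not suffice, because after this procedure it is an expected conduction change.

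The charter should also say whether (b) covers a death that follows a sample taken too early to show a rise, as the existing criterion after 72 hours does.

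If the sponsor prefers no new line, the minimum is a sentence saying that these events are deliberately captured only as death, or as coronary obstruction where that applies.

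The cost is one extra line in the tables and a short charter addition, with no new tests. The total MI rate may be slightly higher than the VARC-defined rate, and the report should say which of the two it quotes.

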**Table 26.2-1: Definitions**

Term	Definition
	
 
• Hemorrhagic Stroke is defined as an acute episode of focal or global cerebral or spinal dysfunction caused by an intraparenchymal, intraventricular, or subarachnoid hemorrhage
 
 
Note 1: The CEC will adjudicate ischemic versus hemorrhagic stroke.
 
Note 2: A stroke may be classified as undetermined if there is insufficient information to allow categorization as ischemic or hemorrhagic
 
Stroke Diagnostic Criteria
 
 
• Rapid onset of a focal or global neurological deficit with at least one of the following: change in level of consciousness, hemiplegia, hemiparesis, numbness or sensory loss affecting one side of the body, dysphasia or aphasia, hemianopia, amaurosis fugax, or other neurological signs or symptoms consistent with stroke
 
• Duration of a focal or global neurological deficit <math>\geq 24</math> h; OR <math>< 24</math> h, if available neuroimaging documents a new hemorrhage or infarct; OR the neurological deficit results in death
 
• No other readily identifiable nonstroke cause for the clinical presentation (e.g., brain tumor, trauma, infection, hypoglycemia, peripheral lesion, pharmacological influences), to be determined by or in conjunction with designated neurologist
 
• Confirmation of the diagnosis by at least one of the following.             
 
○ Neurology or neurosurgical specialist
 
○ Neuroimaging procedure (MRI or CT scan), but stroke may be diagnosed on clinical grounds alone
 
 
 
 
Note 3: Subjects with non-focal global encephalopathy will not be reported as a stroke without unequivocal evidence based upon neuroimaging studies (CT scan or brain MRI).
 
Stroke Definitions
 
Diagnosis as above, preferably with positive neuroimaging study
 
 
• Non-disabling: Modified Rankin Scale (mRS) score <math>< 2</math> at 90 days OR one that does not result in an increase of at least one mRS category from an individual’s pre-stroke baseline
 
• Disabling: Modified Rankin Scale score <math>\geq 2</math> at 90 days AND an increase of at least one mRS category from an individual’s pre-stroke baseline
 
 
Note 4: Modified Rankin Scale assessments should be made by qualified individuals according to a certification process.
 
Note 5: Assessment of the mRS score should occur at all scheduled visits in a study; mRS also should be performed after a stroke and at 90 days after the onset of any stroke.

STRUCTURAL VALVE DETERIORATION	
Component of time-related valve safety defined as follows.
 
 
• Valve-related dysfunction: Mean aortic valve gradient <math>\geq 20</math> mmHg, EOA <math>\leq 0.9</math>-<math>1.1</math> cm^2, and/or DVI <math>< 0.35</math> AND/OR moderate or severe prosthetic valve regurgitation (per VARC definition)
 
• Requiring repeat procedure (TAVR or SAVR).
 

TAV-IN-TAV DEPLOYMENT	
An additional valve prosthesis is implanted within a previously implanted prosthesis because of suboptimal device position and/or function during or after the index procedure.

TRANSIENT ISCHEMIC ATTACK (TIA)	
 
• Transient episode of focal neurological dysfunction caused by brain, spinal cord, or retinal ischemia, without acute infarction
 
• Duration of a focal or global neurological deficit is <math>< 24</math> h
 

Table 26.2-1: Definitions

Term	Definition
	
 
Neuroimaging does not demonstrate a new hemorrhage or infarct (if performed)
 
 
Note: The difference between TIA and ischemic stroke is the presence of tissue damage or new sensory-motor deficit persisting >24 hours. By definition, TIA does not produce lasting disability.

UNANTICIPATED SERIOUS ADVERSE DEVICE EFFECT (USADE)	
Serious adverse device effect which by its nature, incidence, severity, or outcome has not been identified in the current version of the risk analysis report
 
Note: An anticipated serious adverse device effect (ASADE) is an effect which by its nature, incidence, severity, or outcome has been identified in the risk analysis report.

UNPLANNED USE OF CPB	Unplanned use of cardiopulmonary bypass (CPB) for hemodynamic support at any time during the TAVR procedure
VALVE EMBOLIZATION	The valve prosthesis moves during or after deployment such that it loses contact with the aortic annulus.
VALVE MALAPPOSITION	Includes valve migration, valve embolization, ectopic valve deployment, or transcatheter aortic valve (TAV)-in-TAV deployment.
VALVE MIGRATION	After initial correct positioning the valve prosthesis moves upward or downward within the aortic annulus from its initial position, with or without consequences (e.g., regurgitation).
VALVE-RELATED DYSFUNCTION	Mean aortic valve gradient $\geq 20$ mmHg, EOA $\leq 0.9$ - $1.1$ cm  , and/or DVI $< 0.35$ AND/OR moderate or severe prosthetic valve aortic regurgitation (per VARC definition)
VALVE-RELATED SYMPTOMS/CHF REQUIRING HOSPITALIZATION	The need for hospitalization associated with valve-related symptoms or worsening CHF (NYHA Class III or IV) is intended to serve as a basis for calculation of a “days alive outside the hospital” endpoint. Included are heart failure, angina, or syncope due to aortic valve disease requiring intervention or intensified medical management; clinical symptoms of CHF with objective signs including pulmonary edema, hypoperfusion, or documented volume overload AND administration of intravenous diuresis or inotropic therapy, performance of aortic valvuloplasty, institution of mechanical support (intra-aortic balloon pump or ventilation for pulmonary edema), or hemodialysis for volume overload; clear documentation of anginal symptoms AND no clinical evidence that angina was related to coronary artery disease or acute coronary syndrome; documented loss of consciousness not related to seizure or tachyarrhythmia.
VALVE THROMBOSIS	Any thrombus attached to or near an implanted valve that occludes part of the blood flow path, interferes with valve function, or is sufficiently large to warrant treatment. Note that valve-associated thrombus identified at autopsy in a patient whose cause of death was not valve-related or at operation for an unrelated indication should not be reported as valve thrombosis.
VASCULAR ACCESS SITE AND ACCESS RELATED COMPLICATIONS	
Major Vascular Complications
 
 
Any aortic dissection, aortic rupture, annulus rupture, left ventricle perforation, or new apical aneurysm/pseudoaneurysm
 
Access site or access-related vascular injury (dissection, stenosis, perforation, rupture, arterio-venous fistula, pseudoaneurysm, hematoma, irreversible nerve injury, compartment syndrome, percutaneous closure device failure*) leading to death, life-threatening or major bleeding**, visceral ischaemia, or neurological impairment
 
Distal embolization (non-cerebral) from a vascular source requiring surgery or resulting in amputation or irreversible end-organ damage
 
The use of unplanned endovascular or surgical intervention associated with death,
 

